6. SAFETY

6.1 Adverse events

All adverse events (AEs) that occur from day 1 of laser therapy up to and including the 12 week follow up visit (+/- 1 week) must be recorded on the eCRFs and in the patient medical notes.

The severity of symptoms are graded using the Common Terminology Criteria for Adverse Events (CTC) 4.0. The CTC grades 1 through 5 with unique clinical descriptions of severity for each AE based on this general guideline:

- Grade 1: Mild; asymptomatic or mild symptoms; clinical or diagnostic observations only; intervention not indicated.
- Grade 2: Moderate; minimal, local or non-invasive intervention indicated; limiting age appropriate instrumental activities of daily living (ADL).
- Grade 3: Severe or medically significant but not immediately life-threatening; hospitalization or prolongation of hospitalization indicated; disabling; limiting self-care ADL.
- Grade 4: Life-threatening consequences; urgent intervention indicated.
- Grade 5: Death related to AE

Adverse events will be coded using the MedDRA dictionary and presented by preferred term, grouped by system organ class.

Treatment emergent adverse events, i.e. those that occur or worsen on or after first dose of study IMP, will be summarised by grade according to the worst grade experienced since day 1 of laser therapy. Data will also be presented separately for related (possibly, probably, definitely) and unrelated (unrelated, unlikely) events. The occurrence of non-serious adverse events will be tabulated, as required for EudraCT reporting. All data will be presented in the safety population by randomised treatment group.

Example Table 11: All adverse events by type: worst severity reported

	Laser (n =)	Sham (n =)
System Organ Class 1, n (%)		
Preferred Term		
Mild		
Moderate		
Severe		
Life-threatening consequences		
Death		
Total number affected		
Preferred Term		
Mild		
Moderate		
Severe		
Life-threatening consequences		
Death		
Total number affected		
System Organ Class 2, n (%)		
Preferred Term		
Mild		
Moderate		
Severe		
Life-threatening consequences		
Death		
Total number affected		

Example Table 12: Non-serious adverse events by type: worst severity reported (unrelated and unlikely causality)

	Laser (n =)	Sham (n =)
System Organ Class 1, n (%)		
Preferred Term		
Mild		
Moderate		
Severe		
Life-threatening consequences		
Death		
Total number affected		
Preferred Term		
Mild		
Moderate		
Severe		
Life-threatening consequences		
Death		
Total number affected		
System Organ Class 2, n (%)		
Preferred Term		
Mild		
Moderate		
Severe		
Life-threatening consequences		
Death		
Total number affected		

Example Table 13: Non-serious adverse events by type: worst severity reported (possible, probable, and definite causality)

	Laser (n =)	Sham (n =)
System Organ Class 1, n (%)		
Preferred Term		
Mild		
Moderate		
Severe		
Life-threatening consequences		
Death		
Total number affected		
Preferred Term		
Mild		
Moderate		
Severe		
Life-threatening consequences		
Death		
Total number affected		
System Organ Class 2, n (%)		
Preferred Term		
Mild		
Moderate		
Severe		
Life-threatening consequences		
Death		
Total number affected		

Example Table 14: Non-serious adverse events by type: worst severity reported (not assessable)

	Laser (n =)	Sham (n =)
System Organ Class 1, n (%)		
Preferred Term		
Mild		
Moderate		
Severe		
Life-threatening consequences		
Death		
Total number affected		
Preferred Term		
Mild		
Moderate		
Severe		
Life-threatening consequences		
Death		
Total number affected		
System Organ Class 2, n (%)		
Preferred Term		
Mild		
Moderate		
Severe		
Life-threatening consequences		
Death		
Total number affected		

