3.2 Analysis populations

The serious breach

A randomisation schedule was prepared which generated unique coordinates for allocations in a 2-dimensional grid (a 2 digit number of the form (x,y)) – the allocation in the grid at (x,y) corresponded to a treatment allocation (laser or sham). THOR had two grids which had different laser/sham settings:

- grid 1 “Internal SW2 - SW6 in 1 & 2 positions”
- grid 2 “Internal SW2 - SW6 in A & B”.

THOR communicated that the laser machines had been programmed to match grid 1.

As a result of routine laser system testing it became apparent that the randomisation schedule did not match grid 1 (i.e. the allocation recorded in the randomisation log did not always match the laser therapy received). After unblinded testing it was found that the laser machines at all sites had been programmed to match grid 2 and *not* grid 1. At this point 20 participants had commenced laser therapy (involving 5 sites in total). Seven of these 20 participants had received treatment that was opposite to what they would have received in line with grid 1. The seven participants affected continued with the treatment they had started receiving [11]. The randomisation schedule was updated so that subsequent treatment allocations would match grid 2, in line with the machines’ settings. The allocations for the first 20 participants were left unchanged in the randomisation log. The treatment received by the 7 affected participants was documented and stored securely by the NCTU Quality Assurance manager and an extra column was added, by the data manager, to the downloaded randomisation log with the treatment received.

Although the wrong allocation was assigned to seven participants the unique coordinates were generated randomly from the randomisation schedule, hence the allocation procedure was still random and unbiased.

The analyses will follow the intention-to-treat (ITT) principle with the ITT analysis set being modified to allow those participants who received the incorrect treatment at randomisation to be included in the treatment group corresponding to the treatment they received [11].

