Modified Intention-to-treat (mITT) analysis set: This population contains all patients randomised into the study (regardless of their adherence with the entry criteria, regardless of subsequent withdrawal from treatment or deviation from the protocol). However, it is a modified ITT analysis set because it will include participants in the treatment group corresponding to the treatment they randomly received (where the randomised (x,y) coordinates for seven participants were used to generate an allocation from the wrong grid).

Statistical analyses will be conducted on complete cases from the mITT analysis set. Participants will be included in analyses if they attended the visit of interest and have evaluable data for the outcome measure of interest. Evaluable data here is non-missing for all outcome measures listed in Section 2.4 except the three questionnaires MDADI, QLQ-C30 and H&N 35, where simple imputation for missing questionnaire items in accordance with the questionnaire’s scoring manual will be used.

Safety population: For the analysis of safety data all randomised patients who received at least one session of laser therapy will be included.

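### SAP 6.1 groups safety data by randomised arm; read literally, this files the adverse events of seven mis-allocated participants under the treatment they did not receive

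*SAP*

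**What the plan says.** SAP 3.2 describes the serious breach. The laser machines at all sites had been programmed to a different grid from the one behind the randomisation schedule, so that "the allocation recorded in the randomisation log did not always match the laser therapy received". The consequences are set out there:

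- "Seven of these 20 participants had received treatment that was opposite to what they would have received in line with grid 1".
- Once the error was found, these seven were not switched; each stayed on what had been started.
- "The allocations for the first 20 participants were left unchanged in the randomisation log".
- Treatment received was documented separately, and "an extra column was added, by the data manager, to the downloaded randomisation log with the treatment received".

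The same section then defines two analysis sets. The mITT set will "include participants in the treatment group corresponding to the treatment they randomly received". The safety population is defined only by exposure: "For the analysis of safety data all randomised patients who received at least one session of laser therapy will be included". No rule is given for the arm in which a member of the safety population is counted.

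The only grouping rule for safety is in SAP 6.1: "All data will be presented in the safety population by randomised treatment group". Example Tables 11 to 14 have columns headed Laser and Sham without further definition. The serious adverse event listing in SAP 6.2 (Table 15) has a treatment-group column, also undefined.

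**The concern.** After the breach the analysts hold two arm variables that disagree for seven people: the allocation in the log and the added treatment-received column. For the mITT set the SAP says which to use. For safety it does not, and the wording of 6.1 points most naturally to the log. A programmer following 6.1 as written would count events in people who had active laser under sham, and the reverse.

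Safety data should be read by exposure. Protocol 9.3.2 lists adverse events attributed to the laser among the secondary outcomes, and SAP Table 13 is reserved for events judged possibly, probably or definitely related. Attribution to the laser means little if the participant is listed in the other arm. Mixing the arms also tends to hide a difference in harm, which is the unsafe direction. Finally, one report would carry two arm memberships for the same people, one for efficacy and one for safety.

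**Working it through.** The plan gives no figure of its own on this point, so there is none to reproduce. The check has two parts.

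**1. Does the text settle the grouping?**

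| Place | Set | Arm defined by |
|---|---|---|
| SAP 3.2, mITT | all randomised | treatment received, stated for the seven |
| SAP 3.2, safety population | at least one session | not stated |
| SAP 6.1 | safety population | randomised group |
| SAP 6.1, Tables 11 to 14 | safety population | column labels only |
| SAP 6.2, Table 15 | listing | undefined column |

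The 20 participants had all started laser therapy when the error was found, so all seven belong to the safety population. Nothing in 3.2 or 6 carries the treatment-received rule over to it by name. Protocol section 16 also treats randomised allocation and treatment received as different bases for analysis.

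**2. How large would the effect be?**

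Inputs from the SAP: 7 affected, 20 treated at discovery (3.2), 87 randomised (2.6), 1:1 allocation (2.1).

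- Share of those treated at discovery: 7/20 = 35%.
- Share of all randomised: 7/87 = 8.0%.

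Inputs not in the documents, and so assumed: arm sizes by the log, the direction of the swaps, and that all 87 had at least one session.

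Let nL and nS be the arm sizes by the log. Let a be the number logged as laser who received sham, and 7 − a the number logged as sham who received laser. Let pL and pS be the true event risks on laser and sham, with the seven carrying the risk of the treatment they received. The expected risks by log group are:

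- logged laser: pL − (a/nL)(pL − pS)
- logged sham: pS + ((7 − a)/nS)(pL − pS)

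The expected difference by log is then (pL − pS) × [1 − a/nL − (7 − a)/nS].

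Results over every split, a = 0 to 7:

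| Assumed log arms | One extreme | Other extreme |
|---|---|---|
| 44 and 43 | 1 − 7/43 = 0.837 | 1 − 7/44 = 0.841 |
| 40 and 47 | 1 − 7/40 = 0.825 | 1 − 7/47 = 0.851 |

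Illustration with assumed risks of 30% on laser and 10% on sham and log arms of 44 and 43: the true 20-point difference would appear as 20 × 0.837 = 16.7 to 20 × 0.841 = 16.8 points.

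If fewer than 87 had a session, the dilution grows slightly. With 80 treated in equal arms, for example, the factor is 1 − 7/40 = 0.825.

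**The case against.** The strongest reply is that 6.1 already means the mITT grouping. SAP 3.2 introduces the modification as applying to the analyses in general, holds that the allocation procedure remained random, and describes the delivered treatment as randomly received. In that vocabulary the seven were randomised to what they got, and the randomised group is the received group. The SAP also plans no analysis by the logged allocation, so the added column was evidently created to define the arms.

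This reading is possible, and for that reason one cannot say that the events will be misfiled. It does not remove the problem. The modification is attached by name to the mITT set, the safety population is defined separately without it, and 6.1 does not refer back. With two conflicting variables in the data, the sentence has to say which one applies.

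Other parts of the reply also stand:

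- The safety output is descriptive, with no formal comparison of arms specified, and the primary analysis is untouched.
- The 0.84 is an expectation. With seven people the realised shift could go either way; for a rare event, one misfiled case turns 1 against 0 into 0 against 1.
- A reader might infer a fixed 16% loss however the seven divide. That is exact only for equal arms, which the documents do not report.
- A reader might blame 6.1 for different denominators in the efficacy and safety tables. The two sets are defined differently, so denominators can differ by design; only the difference in arm membership comes from 6.1.
- A reader might count Table 15 as wrong. It has an undefined column, which is a gap and not a shown error.

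**Conclusion.** The point holds as a defect in the wording of 6.1. Taken literally, the sentence assigns seven participants (8% of those randomised) to the arm whose treatment they did not receive and conflicts with the mITT grouping in 3.2. The stronger conclusion, that their adverse events will certainly be reported in the wrong arm, is not supported, because the authors may have intended the mITT membership.

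If the log were used, a true difference in adverse-event risk would on average be reduced to about 0.84 of its size, or between 0.825 and 0.851 with arms of 40 and 47. This assumes that nearly all 87 started treatment and that the seven had the risks of the treatment they received. The conflict in the text does not depend on these assumptions; only its size does.

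**What to change.** In SAP 6.1, replace the grouping clause with wording such as: *Safety results are shown by treatment received, using the same arm membership as the mITT set, taken from the treatment-received column added to the downloaded randomisation log.* Apply this to Tables 11 to 14, and define the treatment-group column of Table 15 in 6.2 in the same way. It would also help to add the grouping rule to the definition of the safety population in 3.2.

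The cost is about one sentence and a column definition. The variable already exists, so no new data are needed and the efficacy analyses do not change. The change should be made before the safety tables are run.

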9.3 Outcome Measures

9.3.1 Primary outcome measure

Primary Outcome: OMWQ-HN score at week 6 following start of LLLT treatment.

9.3.2 Secondary outcome measures:

- OMWQ-HN and WHO mucositis scores collected at baseline and weekly during weeks 1-6 of treatment.
- Long term reported health related quality of life as measured by EORTC QLQ C30 (version 3.0),
 EORTC QLQ C30/H&N 35 (EORTC QOL Module for Head and Neck Cancer) and the EQ-5D-5L at baseline, week 6, month 4 and month 14, and MDADI at baseline, week 6, month 4 and month 14.
- Nutritional Parameters as measured by Performance Status Scale's (PSS-HN) collected weekly
 at baseline, weeks 1-6, month 4 and month 14. Recording of weekly weight changes from
 baseline during treatment, the quantity of enteral nutrition consumed, number of days of
 feeding tube in situ.
- Changes in swallowing function measured by the timed water swallow test collected at baseline, week 6 of LLLT month 4 and month 14.
- Pain outcomes as measured by use of analgesics/ topical treatment and pain domain of EQ 5D-5L and OMWQ-HN at randomisation and weekly to week 6 during treatment.

 Safety, specifically adverse events attributed to LLLT and clinical complications notably number of days as inpatient hospital admissions and interruptions in CRT treatment (recorded weekly 1-6 during treatment).

• Clinical outcomes specifically patient survival, quality-adjusted survival recurrence and persistence of disease at 14 months.

Economic outcomes:

- Incremental cost per change in OMWQ-HN score recorded between baseline and at week 6 of therapy and incremental cost per QALY over 14 months
- Quality-adjusted life years based upon EQ-5D-5L [14] and EORTC-8D [15] utility scores measured at baseline, week 6 and 4 and 14 months
- Costs associated with treatment (weeks 0-6) will be collected weekly via the eCRFs
 (e.g. adverse events and use of analgesics)
- Health care utilisation based on responses to Health Utilisation Questionnaire administered at 4 and 14 months (assessing: visits to the GP/walk-in clinic/A&E etc.)
- Participant and family costs collected via the Time and Travel Questionnaire administered at 14 months
- Total costs of LLLT and sham LLLT measured at 4 and 14 months, from the perspective of the NHS and personal and social services to participants and families

Qualitative outcomes as identified through:

- Observations of training
- Interviews with health professionals delivering LLLT

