16. STATISTICAL CONSIDERATIONS

Definitions of outcome measures, scoring procedures and derivations of overall and domain scores for the primary outcome OMWQ-HN score and secondary measures of WHO mucositis score, EORTC QLQ C30 (version 3.0) EORTC H&N 35, EQ-5D 5L (version 1.0) are presented in Appendix 4.

Adverse events are coded according to MEDRA coding with severity coded according to WHO CTC 4.0 grading system.

Survival is defined as date of randomisation to date of death from any cause, survivors censored at their date of last follow-up visit.

Time to recurrence is defined as date of randomisation to date of clinical recurrence for patients with confirmed date of clinical recurrence or patients with confirmed disease related death - survivors who are recurrence-free and patients who have died from other causes are censored at their date of last follow-up visit.

Primary analyses are carried out on an intention to treat, retaining all randomised patients in the analysis according to their randomised treatment allocation, and a complete case basis. Sensitivity analyses may be performed on a per protocol basis, according to treatment received, and on an imputed dataset, should missing data deem this necessary. Treatment related adverse events will be reported in all patients starting treatment.

A full analysis plan will be in place prior to any comparative analyses, and will be reviewed by the oversight committees.

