6.2 Serious adverse events

Example Table 15: Line listing of serious adverse events

SAE number	Patient ID	Treatment group	Laser start date	Laser end date	SAE onset date	Description	Severity ^A	Action ^B	Causality ^C	Expected	Resolution date

A: Mild/Moderate/Severe/Life-threatening consequences/Death
 B: None/ Treatment adjusted or interrupted/Treatment discontinued/Concomitant medication/Non-drug therapy given/Hospitalisation
 C: Unrelated/Unlikely/Possible/Probable/Definitely/Not assessable

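### The causality-split adverse event tables are limited to non-serious events, so no planned table gives, by arm, the number of participants with any LLLT-related event or with a related serious event

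*SAP*

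**What the plan says.** Protocol section 9.3.2 lists among the secondary outcomes "Safety, specifically adverse events attributed to LLLT and clinical complications". Protocol section 16 adds "Treatment related adverse events will be reported in all patients starting treatment". Neither statement is limited by seriousness.

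SAP section 6.1 says that treatment-emergent events will be summarised by worst grade, and then: "Data will also be presented separately for related (possibly, probably, definitely) and unrelated (unrelated, unlikely) events". A separate sentence deals with registry output: "The occurrence of non-serious adverse events will be tabulated, as required for EudraCT reporting".

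The example shells that follow are:

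- "Example Table 11: All adverse events by type: worst severity reported", with Laser and Sham columns and severity rows up to death.
- "Example Table 12: Non-serious adverse events by type: worst severity reported (unrelated and unlikely causality", with the same layout.
- Table 13, "Non-serious adverse events by type: worst severity reported (possible, probable, and definite causality", with the same layout.
- Table 14, for non-serious events whose causality could not be assessed, with the same layout.

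SAP section 6.2 consists of one shell, "Example Table 15: Line listing of serious adverse events". Its columns include treatment group, severity, causality and expectedness.

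**The concern.** The text of section 6.1 and the shells beneath it describe different analyses. The text splits all treatment-emergent events by relatedness and treats the non-serious tabulation as a separate registry requirement. In the shells the two are merged, so every causality-split table carries the non-serious restriction.

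If the shells are programmed as titled, a serious event judged possibly, probably or definitely related adds nothing to Table 13. A participant whose related events were all serious is absent from it. A participant with both a serious and a non-serious related event under the same term appears at the worst grade of the non-serious one.

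At stake is the summary of a named secondary outcome: how many participants in each arm had harm attributed to the laser. The case is not remote. Protocol section 15.2.1 lists a short-term increase in mucositis symptoms as an expected event after LLLT, and section 15.2 expects some admissions for mucositis in this population. An admission makes an event serious under section 15.1.

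**Working it through.** The plan gives no figure to reproduce, so the check sets the outputs side by side and asks which of them could yield the two counts of interest.

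| Output | Events covered | Aggregated by arm | Causality shown | Serious events identifiable |
|---|---|---|---|---|
| Table 11 | All, on its title | Yes | No | No |
| Tables 12 to 14 | Non-serious only | Yes | Yes | Not applicable |
| Table 15 | Serious only | No; arm shown per event | Yes, per event | Yes |

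**Step 1: can Table 11 supply the count of related events?** No, because it has no causality split. Nor can it supply a count of serious events, because severity does not stand in for seriousness. Hospitalisation alone makes an event serious (protocol 15.1), and the severity codes for Table 15 include mild and moderate.

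**Step 2: do the time windows match?** Adverse events are recorded from day 1 of laser therapy to the week 12 visit (SAP 6.1). Serious events are recorded to the month 14 visit (protocol 15.2). Participants who started laser therapy after 6 July 2018 had a last visit at month 4 (SAP Table 1), which is still later than week 12. The SAP does not say whether Table 11 includes serious events after week 12. If it does not, those events appear only in the listing.

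**Step 3: can Tables 13 and 15 be combined?** For one arm, let N be the participants with at least one non-serious related event, S those with at least one related serious event, and B those with both. The number with any related event is

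R = N + S − B.

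S can be counted by hand from Table 15. B cannot be obtained, because Table 13 carries no participant identifiers. The two outputs therefore only bound R between max(N, S) and N + S. The shells also have no row for participants with an event of any type, so N itself is available only term by term.

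**Step 4: size of the undercount.** Table 13 reflects N where the outcome calls for R. The participants missed are O = R − N = S − B, those whose related events were all serious. The proportional undercount is O / R, which can lie anywhere from 0 to 1.

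For scale only, assume that the 87 randomised participants split evenly and that all started laser therapy, giving 87 / 2 = 43.5 per arm. Each participant missed then takes the following from the arm's percentage:

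- O = 0: 0.0 percentage points
- O = 1: 1 / 43.5 = 2.3 percentage points
- O = 2: 2 / 43.5 = 4.6 percentage points
- O = 3: 3 / 43.5 = 6.9 percentage points

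These values of O are assumptions. The documents give no expected number of related serious events.

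**Step 5: are the rows consistent with the titles?** Death is a seriousness criterion in protocol 15.1, so the death row of a non-serious table must be empty. The life-threatening row is different. It follows CTC grade 4, whose definitions are set event by event, whereas protocol 15.1 requires immediate risk of death at the time of the event. A grade 4 event need not meet that criterion, so this row may legitimately hold entries.

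**The case against.** The strongest reply has four parts.

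First, the text of 6.1 governs and the shells are only labelled as examples. This stands as a reading of intent. A reader might infer that the SAP chose to leave serious related events out of the causality analysis, and the text does not support that. But the text and shells then disagree, and a programmer working from the shells would produce the narrower tables.

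Second, a reader might infer that serious events are never counted by arm. Table 11, on its title, contradicts that. What remains missing is causality, a seriousness flag and a stated end date.

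Third, the listing carries arm and causality, and with 87 participants a count is easily made; protocol 15.2 also requires serious events to be reported by relatedness. This largely stands: the information is not lost. It does not supply the combined count R, and protocol 15.2 does not ask for a summary by arm. It also assumes that the listing is complete. Protocol 15.2.1 exempts expected serious events from the SAE form although 15.2 requires all serious events to be reported, and the SAP does not name the listing's source. The SAP cites protocol version 4.0 and the text reviewed is version 2.1, so that tension may have been resolved.

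Fourth, related serious events may be rare. Protocol 15.2 expects most events, serious or not, to stem from the (C)RT. This stands, and it is why no size can be claimed.

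Nor is the row for total number affected wrong in Tables 12 to 14: it is correct for a non-serious table, only narrower than the outcome.

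**Conclusion.** The point holds as a mismatch between the SAP's text and its shells. The protocol outcome and the 6.1 text call for related events without a seriousness limit. All three causality-split shells impose one, and no planned table gives the by-arm number of participants with any LLLT-related event or with a related serious event.

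Read as titled, Table 13 excludes every related serious event. How many participants that removes is unknown and may be none. The conclusion assumes that the shells are programmed as titled. If the programmers follow the text of 6.1 instead, the undercount disappears, but the shells are then mislabelled and still need correcting. The documents do not support the larger claims that serious events go uncounted by arm or that a particular percentage of related harm is missed.

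The change is worth making: it concerns a named secondary outcome, it gives a count that the planned outputs cannot, and it is cheap.

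**What to change.** 1. Make Tables 12 to 14 cover all treatment-emergent adverse events, serious and non-serious, by causality, as the 6.1 text says. Include a first row for participants with at least one event of any type.
2. Add to section 6.2 one by-arm summary of serious events giving participants and events, overall and related. Keep the listing, and state its data source.
3. Keep a separate non-serious table for registry reporting. Drop only its death row; retain the grade 4 row.
4. State whether Table 11 includes serious events and up to what date, given the different windows for adverse events and serious adverse events.

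The cost is edited table shells, a short addition to the SAP text and a few lines of code. No new data are needed, because arm, severity and causality are already planned fields.
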